### **3.1.3 HDAC inhibitors: Clinical Activity in Lymphoid Malignancies**

#### **3.1.3.1 Cutaneous T-cell Lymphoma (CTCL)**

The clinical activity of romidepsin was first demonstrated in a National Cancer Institute (NCI) phase I study. [Sandor V, 2002] Three patients with CTCL and 1 with significant cutaneous involvement of peripheral T-cell lymphoma (PTCL) all demonstrated a response to romidepsin at varying dose levels (12.7 to 17.8 mg/m^2). The patient with PTCL experienced a complete remission after 8 cycles of romidepsin. Subsequently, romidepsin was further evaluated in 135 evaluable subjects with CTCL in Study GPI-04-0001 and NCI Study 1312. [Rasheed W, 2008] Across all 135 evaluable subjects with CTCL, the overall response rate (ORR) was 41% (55/135) and the complete response (CR) rate was 7% (10/135). Subjects with advanced disease had a similar ORR as subjects with earlier stage disease: 42% for  $\geq$ Stage IIB and 38% for Stage I or IIA disease. Romidepsin was active in all sites of disease, including skin, lymph nodes, viscera, and blood. The median duration of response was 454 days (14.9 months). Although the median time to response was 57 days (1.9 months), in some cases an objective response to romidepsin was achieved after  $\geq$ 6 months. Across all 135 subjects included in the pooled evaluable subjects analysis set, median time to disease progression was 252 days (8.3 months). In Study GPI-04-0001, treatment alleviated pruritus in most subjects (48 of 52, 92%) who entered the study with this symptom. These data led to FDA approval of romidepsin for CTCL in September, 2009.

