#### **3.1.3.2 Peripheral T-cell lymphoma (PTCL)**

In the initial Phase 2 NCI-sponsored study in 48 subjects with PTCL or other T-cell lymphomas were enrolled in addition to the CTCL patients listed above. [Piekacz R, 2005] Among all 48 subjects, the ORR (CR+PR) was 31% (15/48). The CR and PR rates were 8% (4/48) and 23% (11/48), respectively. When response was evaluated among the 34 subjects who received  $\geq$ 2 cycles of therapy, the ORR was 44% (15/34) and the CR and PR rates were 12% (4/34) and 32% (7/34), respectively.

This activity of romidepsin in PTCL was confirmed in the multi-center Phase 2 study, where 131 patients with relapsed PTCL. [Coiffier B, 2011] The objective response rate was 25% (33/130), including 15% (19/130) with CR/CRu. Response rates were not impacted by patient characteristics, prior stem-cell transplant,

number or type of prior therapies, or response to last prior therapy. The median duration of response was 17 months, with the longest response ongoing at 34+ months. Of the 19 patients who achieved CR/CRu, 17 (89%) had not progressed at a median follow-up of 13.4 months. The most common grade  $\geq 3$  adverse events were thrombocytopenia (24%), neutropenia (20%), and infections (all types, 19%). This data led to FDA approval of romidepsin for PTCL in June of 2011.

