**\*1 cycle equals 28 days**

### **9.3 Treatment Plan romidepsin/lenalidomide Phase IIa**

The entire accrual is planned to have up to 51 patients in the phase IIa portion; each disease cohort will have 15 patients (B-cell lymphoma, multiple myeloma or PTCL). There will be an expansion of the T-cell cohort to include an additional 6 patients with acute T-cell leukemia/lymphoma. After a sufficient number of patients have been enrolled for determination of the primary and secondary objectives, cohorts may be closed to accrual by the MSK principal investigator. The MTD for lymphoma has been determined to be 14mg/m^2 romidepsin on Days 1, 8, 15 and 25mg lenalidomide from Days 1-21. The patients treated at MTD in the phase Ib cohort (if measurable disease at enrollment) and phase IIa cohort will be evaluated both collectively and by disease subtype. Patients with more than one histology are eligible and will be assigned by the principal investigator to a specific disease subtype.

- In patients with MM, due to the presence of toxicities, patients will be dosed at romidepsin 10mg/m^2 and lenalidomide 25mg (see table 2a). If two of six (or fewer) patients treated at this dose level develop dose-limiting toxicities, the initial dosing for subsequent patients will be decreased to romidepsin

10mg/m^2 and lenalidomide 15mg. For example, if two of four patients treated at this initial dose develop dose-limiting toxicities, the starting dose for subsequent patients will be reduced as above.

- At a starting dose of romidepsin 10mg/m^2 and lenalidomide 15mg, should 2 of 6 (or less) patient will be reduced to romidepsin 8mg/m^2 and lenalidomide 15mg.
- At a starting dose of romidepsin 8mg/m^2 and lenalidomide 15mg, should 2 of 6 (or less) patients have dose-limiting toxicities, the initial dose for subsequent patients will be reduced to romidepsin 8mg/m^2 and lenalidomide 10mg.

Table 2a: Multiple Myeloma Dosing for Phase IIa Portion

Dose level	Romidepsin	Lenalidomide
1	10	25
-1	10	15
-2	8	15
-3	8	10

The treatment plan for the phase IIa portion is described below:

Romidepsin/Lenalidomide Cycle 1 Day 1 + subsequent Cycle X

Romidepsin MTD IVPB over 4 hours

Lenalidomide MTD PO q days 1-21

Romidepsin/Lenalidomide Cycle 1 Day 8

Romidepsin MTD IVPB over 4 hours

Romidepsin/Lenalidomide Cycle 1 Day 15

Romidepsin MTD IVPB over 4 hours

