 Lymphoma: CT including at least the chest, abdomen and pelvis or PET/CT is required for response (systemic B and T-cell lymphoma patients only) assessment. A bone marrow will only be repeated to confirm a complete response if previously known to be involved. Cutaneous T-cell lymphoma patients will have imaging at baseline and (CTCL) will have an mSWAT (Appendix I) performed monthly for the first three cycles and then at each response assessment timepoints (end of cycle 4, 6 and thereafter at the end of every third cycle). In CTCL patients, imaging will be repeated if appropriate (patients with known nodal or visceral disease) every other cycle. Sezary panel in patients with Sezary syndrome. Cutaneous lymphoma patients without nodal or visceral disease will have imaging repeated only to confirm a complete response. After cycle 12, patients on continuous therapy may be imaged as clinically indicated, at the discretion of the treating physician. At discontinuation of therapy, end of study response assessments – including imaging – should be performed.

Serum/urine protein electrophoresis, serum/urine immunofixation, quantitative immunoglobulins, and serum free light chains are required if appropriate for (multiple myeloma patients only) response assessment. A bone marrow will only be repeated if to confirm a complete response. Patients with non-secretory myeloma will have the bone marrow assessment repeated if they have been otherwise clinically stable (i.e. without new lytic lesions, soft-tissue plasmacytomas or hypercalcemia). A skeletal survey is allowed to rule out bone lesions for evaluation of disease progression and to confirm a complete response in nonsecretory multiple myeloma. PET/CT should be performed at screening and to confirm responses in patients with soft tissue plasmacytomas.

 An additional safety assessment will be done 28 days (+/- 2 days) following the last dose of protocol therapy.

 If romidepsin is omitted on day 8 per dose reduction algorithm (Table 4) then hematologic and electrolyte assessments are not required.

Response assessment will be performed at the end of cycles 2, 4, and 6. Thereafter, response assessment will occur at the end of every third cycle (9,12,15, etc.) until disease progression or removal from study. Myeloma patients will have their disease assessed after each cycle.

 +/- 3 days

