### **12.2.1 Extracutaneous Response Criteria**

Response criteria will be based on assessment following every 2 cycles for 6 months and then every 3 cycles thereafter. The criteria are as follows (GTD = Greatest Transverse Diameter; SPD = Sum of the Products of the Greatest Diameter):

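### Imaging becomes discretionary after cycle 12, against the every-third-cycle schedule stated elsewhere, so progression in long-term lymphoma responders can be dated late

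*Combined protocol and SAP*

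**What the plan says.** Three places in the protocol govern lymphoma assessment late in treatment.

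- Table 7 Legend, footnote 7, first states that "CT including at least the chest, abdomen and pelvis or PET/CT is required for response (systemic B and T-cell lymphoma patients only) assessment". Later in the same footnote it says "After cycle 12, patients on continuous therapy may be imaged as clinically indicated, at the discretion of the treating physician", and then "At discontinuation of therapy, end of study response assessments – including imaging – should be performed".
- Table 7 Legend, footnote 11, on the period once the first six cycles are over: "Thereafter, response assessment will occur at the end of every third cycle (9,12,15, etc.) until disease progression or removal from study". Patients with myeloma are assessed after every cycle.
- Section 12.2.1: "Response criteria will be based on assessment following every 2 cycles for 6 months and then every 3 cycles thereafter". No end point is given.

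Section 12.2.1 defines extracutaneous progression by growth in node size or by a new lesion. Section 4.1 ends DOR at progression, change of therapy, death or last contact, and bases EFS on documented progression, change in therapy or death. Section 14.0 plans Kaplan-Meier or competing-risks summaries of both, and gives no rule for dating a progression found between irregular scans.

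**The concern.** A site cannot complete the cycle-15 assessment named in footnote 11 without the scan that footnote 7 leaves to the physician. Different centres can read this differently. A site that follows footnote 7 has no fixed scan interval in the period when the protocol's own background suggests many responders would progress. Extracutaneous progression rests mainly on imaging, so a longer gap between scans moves the recorded date later. The gap would also vary by physician.

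DOR and EFS are stated secondary objectives, and section 4.1 says phase IIa is to give background for a possible subtype-specific phase II study. An inflated DOR would carry into that planning.

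**Working it through.** **Inputs.** Cycle length is from section 9.3 ("1 cycle equals 28 days"). Romidepsin in CTCL (section 3.1.3.1): median DOR 454 days, median time to response 57 days, median time to progression 252 days. Romidepsin in PTCL (section 3.1.3.2): "The median duration of response was 17 months, with the longest response ongoing at 34+ months". Lenalidomide in indolent B-cell lymphoma (section 3.2.3.3): median DOR not reached, longer than 16.5 months.

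**Reproducing the protocol's figures** at 30.4375 days per month: 454 / 30.4375 = 14.9; 57 / 30.4375 = 1.9; 252 / 30.4375 = 8.3 months. All match the text.

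**End of cycle 12.** 12 × 28 = 336 days; 336 / 30.4375 = 11.0 months. This is a minimum, because cycles can be delayed. All three quoted DOR medians exceed it before any time to response is added. The analysis in section 14.0, 18 months after the last enrolment, comes later still.

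**Where the median progression of responders falls, from treatment start.**

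- CTCL: 57 + 454 = day 511 (511 / 28 = 18.3 cycles).
- PTCL: 17 months = 517 days. Assuming response at day 56, 56 + 517 = day 573 (20.5 cycles).
- Indolent B-cell: 16.5 months = 502 days. On the same assumption, after 56 + 502 = day 558 (19.9 cycles).

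**Share of responders not yet progressed at day 336**, assuming exponential durations: 0.5^((336 − response day) / median DOR).

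| Case | Calculation | Share |
|---|---|---|
| CTCL, response at day 57 | 0.5^(279/454) | 0.653 |
| Indolent B-cell, response at day 56 | 0.5^(280/502) | at least 0.679 |
| PTCL, response at day 56 | 0.5^(280/517) | 0.687 |
| CTCL median, response at end of cycle 4 (day 112) | 0.5^(224/454) | 0.710 |
| PTCL median, response at day 112 | 0.5^(224/517) | 0.741 |

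Footnote 7 covers only patients on continuous therapy. If a fraction f of these unprogressed responders is still on treatment, the share exposed to discretionary imaging is about 0.65f to 0.74f. The documents do not give f.

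**All patients rather than responders.** With the CTCL median time to progression of 252 days, the share progression-free at day 336 is 0.5^(336/252) = 0.397. The median lies before the end of cycle 12.

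**Dating delay.** Footnote 7 states no interval, so intervals must be assumed. Progression times were simulated with the CTCL and PTCL medians and with scans at days 56, 112, 168, 252 and 336, then at a fixed spacing. The mean delay for a progression after day 336 was:

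| Spacing after cycle 12 (days) | Mean delay (days) |
|---|---|
| 84 (every third cycle) | 43 |
| 126 | 65 |
| 168 | 87–88 |
| 252 | 133–134 |
| 336 | 180–182 |

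Against the 84-day schedule, the extra delay runs from 65 − 43 = 22 to 182 − 43 = 139 days. The observed median DOR moved less regularly: it was 532 or 616 days depending on where the scan dates fell, a shift of 0 or 84 days. The mean delay is the steadier measure.

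**The case against.** The strongest reply is that this is a wording conflict whose effect on the endpoints is unproven. Several parts of that reply stand.

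- A reader might infer that two thirds or more of DOR events fall in the discretionary period. The calculation does not show that. It gives responders not yet progressed at day 336. Those who stop earlier for toxicity, withdrawal or a change of therapy are outside the footnote 7 sentence, and change of therapy is itself a DOR event.
- A reader might infer that scans will be done only for symptoms and that dates will be late. The text allows any clinical indication, and a physician may still scan every 84 days. Physical examination and, in lymphoma, LDH remain on day 1 of later cycles and can prompt a scan. Imaging at discontinuation is a backstop, though it acts only once therapy stops.
- CTCL skin disease keeps mSWAT at every third cycle with no stop at cycle 12, so the CTCL duration comes from a group largely outside the problem. All the durations are single-agent, and none is given for aggressive B-cell lymphoma, Hodgkin lymphoma or acute T-cell leukemia/lymphoma.
- A reader might blame footnote 7 for pooling myeloma and lymphoma under different assessment frequencies. That difference exists from the first cycles.
- DOR and EFS are secondary, single-arm and descriptive. The primary dose and safety objective is untouched.

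None of this removes the contradiction, or the possibility of late dating where progression is read from scans.

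**Conclusion.** The conflict is real and must be reconciled. In systemic, nodal or visceral lymphoma, following footnote 7 can date progression late and at times that depend on the physician. That can overstate DOR in long-term responders and lift the tail of EFS.

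The size is conditional. The 65% to 74% rests on exponential durations, single-agent medians and assumed response times, and it is an upper limit on the share exposed, because some of those responders will have left treatment. The extra delay of about 22 to 139 days per late progression rests wholly on assumed scan spacings.

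The documents do not support the stronger conclusion that EFS as a whole will be overstated. With a median time to progression of 252 days in CTCL, median EFS would probably move little. CTCL skin disease and myeloma are largely unaffected.

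**What to change.** Reconcile footnote 7 with footnote 11 and section 12.2.1 so that one imaging schedule governs after cycle 12 for patients with systemic, nodal or visceral lymphoma. State the scope of the footnote 7 sentence as well: it follows the CTCL text, and it is unclear whether it covers all lymphoma.

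If discretionary imaging is retained, add to section 14.0 a sensitivity analysis of DOR and EFS that treats a progression after cycle 12 as interval-censored between the last negative and the first positive scan. Report the actual scan intervals beside it.

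Do not make censoring at the last on-schedule assessment the main rule. It would discard later-detected progressions and could censor many responders near cycle 12, leaving median DOR hard to estimate. It also conflicts with interval censoring of the same events.

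The cost is a footnote edit plus either some scans in the patients still on treatment after cycle 12, or one small extra analysis and a stated DOR that may come out shorter.

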## 11.0 TOXICITIES/SIDE EFFECTS

### 11.1 Side Effects of Romidepsin

#### Likely

- Nausea
- Vomiting
- Loss of appetite
- Fatigue
- Constipation
- Diarrhea
- Altered sensation of taste
- Fever

#### **Side effects related to levels of substances found in the blood:**

- Thrombocytopenia
- Anemia
- Decreased white blood cells
- Increased levels of glucose
- Decreased calcium
- Decreased magnesium
- Decreased albumin

#### Less Likely

- Swelling
- Decreased weight
- Heart tracing irregularities
- Weakness
- Joint pain
- Itching
- Back pain
- Dizziness
- Abdominal pain
- Dehydration
- Changes in heart function
- Heartburn
- Low blood pressure
- Cough
- Skin infections
- Shortness of breath
- Headache
- Lack of energy
- Insomnia
- Neuropathy

#### **Side effects related to levels of substances found in the blood:**

- Decreased potassium
- Decreased lymphocytes
- Increased creatinine

- Decreased sodium
- Increased magnesium
- Decreased phosphate
- Increased liver and bone enzyme tests

**Rare but serious**

- Anxiety
- Infections which can be serious
- Bleeding
- Increased heart rate

**Side effects related to levels of substances found in the blood:**

- Increased potassium
- Increased uric acid
- Deep vein thrombosis

As of September 2010, with 891 patients having received romidepsin as a single agent, 39 of 447 (9%) of patients with hematologic malignancies and 36 of 444 (8%) of patients with solid tumors have died from an adverse event during treatment with romidepsin. Not unexpectedly, the most common cause was related to the patients' underlying disease. Death as a result of disease progression has been reported in 9 (2%) of the patients with hematologic malignancies and in 24 (5%) of the patients with solid tumors. The cause of death was not otherwise specified in 2 (0.4%) of the patients with hematologic malignancies and in 4 (0.9%) of the patients with solid tumors. All other causes of death have been reported in less than <1% in either indication.

**11.2 Side Effects of Lenalidomide**

**Likely:**

- Fatigue or feeling tired
- Lack or loss of strength
- Anemia or a decrease in red blood cells that can cause tiredness
- Decrease in white blood cells that can make you more prone to infections (Neutropenia)
- Decrease in platelets which can cause you to bruise or bleed easily (Thrombocytopenia)
- Blood clot in lower extremities
- Vision blurred
- Nosebleed
- Constipation or difficulty moving your bowels
- Diarrhea or loose/frequent bowel movements
- Nausea or vomiting
- Loss of appetite
- Joint pain
- Swelling of the arms and legs
- Fever

- Cough
- Shortness of breath or difficulty catching your breath
- Upper respiratory infection (infection of nose, sinus, and throat)
- Allergic reaction
- Itching and dry skin
- Dizziness
- Headache
- Altered sense of taste
- Abnormal sense of touch
- Pain and decreased sensation in nerves
- Pneumonia

**Less Likely:**

- Problem with moving food through digestive system (gastrointestinal motility disorder)
- Dry mouth
- Indigestion (dyspepsia)
- Muscular weakness
- Stroke
- Tingling sensation (paresthesia)
- Fainting (syncope)
- Drowsiness
- Difficulty breathing (respiratory distress)
- Excessive sweating (hyperhidrosis)
- Fever with a decrease in white blood cells that help fight infections (febrile neutropenia)
- Shortage of all types of blood cells including red blood cells, white blood cells, and platelets (pancytopenia)
- Excessive loss of body water (dehydration)
- High blood sugar (hyperglycemia)
- Uncontrolled blood sugar (diabetes mellitus)
- Higher than normal blood uric acid (hyperuricemia)
- Higher than normal level of iron in body (iron overload)
- Lens of eye becomes cloudy (cataracts)
- High blood pressure (hypertension)
- Low blood pressure (hypotension)
- Bleeding
- Altered mood
- Depression
- Irregular heartbeat (atrial fibrillation)
- Failure of the heart (cardiac failure)
- Heart attack (acute myocardial infarction)
- Fast heartbeat (tachycardia)
- Not enough blood flow to heart muscle (myocardial ischemia)
- Secondary cancer

- Kidney damage (renal failure)
- Abnormal liver function tests
- Tumor lysis syndrome

### **Rare but Serious**

- Fever with a decrease in white blood cells that help fight infections (Febrile neutropenia)
- Blood clot in or around the lungs (Pulmonary embolism)
- Deep vein thrombosis or blood clots in larger blood vessels
- Atrial fibrillation or irregular heartbeat
- Pneumonia or an infection of the lungs
- Sepsis or an infection of the blood
- Kidney failure or inability of the kidneys to remove waste from the body
- Muscle breakdown (rhabdomyolysis)
- Swelling of the lungs
- Severe skin rash (Stevens-Johnson syndrome)

The following events have been reported during the use of lenalidomide in clinical studies and in the post-marketing setting:

The rare adverse event of angioedema and serious skin reactions including Stevens-Johnson syndrome (SJS) and toxic epidermal necrolysis (TEN) have been reported. These events have the potential to result in death. Medical journals have reported patients with allergic skin reaction with thalidomide who also developed the same type of reaction with lenalidomide. The rare adverse event of rhabdomyolysis has been observed with lenalidomide.

Tumor lysis syndrome and tumor flare reaction have commonly been observed in patients with Chronic Lymphocytic Leukemia (CLL), and uncommonly in patients with other lymphomas, who were treated with lenalidomide. Fatal instances of TLS have been reported during treatment with lenalidomide. There have been rare reports of TLS in patients with multiple myeloma treated with lenalidomide, and no reports in patients with myelodysplastic syndrome treated with lenalidomide.

### **11.3 Second new cancers**

According to researchers, patients with cancer have a higher risk of developing a second new cancer when compared to people without cancer. In clinical studies of newly diagnosed multiple myeloma, a higher number of second cancers were reported in patients treated with induction therapy and/or bone marrow transplant then lenalidomide for a long period of time compared to patients treated with induction therapy and/or bone marrow transplant then no lenalidomide.

### **11.4 Other Risks**

Patients should be instructed that if any physician other than the study doctor prescribes medication for another condition, or patients start to take any over-the-

counter medications or vitamins, they must inform the study staff. This is important because the interaction of some medications may cause serious side effects.

- Patients taking lenalidomide and dexamethasone for multiple myeloma should be careful taking drugs that may increase chance of having blood clots.
- Cases of transient liver laboratory abnormalities were reported in patients treated with lenalidomide.
- Lenalidomide has been shown to increase the level of digoxin in the blood in some patients.

## **11.5 Risks Associated with Pregnancy**

### **Pregnancy Risk:**

Lenalidomide is related to thalidomide. Thalidomide is known to cause severe life-threatening human birth defects. Findings from a monkey study indicate that lenalidomide caused birth defects in the offspring of female monkeys who received the drug during pregnancy. If lenalidomide is taken during pregnancy, it may cause birth defects or death to any unborn baby. Females must not become pregnant while taking lenalidomide. Patients with multiple myeloma who take lenalidomide and dexamethasone have a greater chance of having blood clots. Because of this, it is recommended patients not take birth control pills or hormone replacement therapy before discussing with the investigator and considering the risks and benefits of these choices.

When taking lenalidomide, the drug is present in semen of healthy men at very low levels for three days after stopping the drug. For patients who may not break down the drug normally, such as patients who do not have normal kidney function, lenalidomide may be present for more than three days. To be safe, all male patients should use condoms when engaging in sexual intercourse while taking lenalidomide, when temporarily stopping lenalidomide, and for 28 days after permanently stopping lenalidomide treatment if their partner is either pregnant or able to have children.

Patients should not donate blood during treatment therapy or for 28 days following discontinuation of lenalidomide.

